2.5 FREQUENCY OF TUMOR RE-EVALUATION

Frequency of tumor re-evaluation while on treatment should be protocol specific and adapted to the type and schedule of treatment. However, in the context of Phase II studies where the beneficial effect of therapy is not known, follow-up every 6–8 weeks (timed to coincide with the end of a cycle) is reasonable. Smaller or greater time intervals than these could be justified in specific regimens or circumstances. The protocol should specify which organ sites are to be evaluated at baseline (usually those most likely to be involved with metastatic disease for the tumor type under study) and how often evaluations are repeated. Normally, all target and non-target sites are evaluated at each assessment. In selected circumstances certain non-target organs may be evaluated less frequently. For example, bone scans may need to be repeated only when complete response is identified in target disease or when progression in bone is suspected.

After the end of the treatment, the need for repetitive tumor evaluations depends on whether the trial has as a goal the response rate or the time to an event (progression/death). If 'time to an event' (e.g., time to progression, disease-free survival, progression-free survival) is the main endpoint of the study, then routine scheduled reevaluation of protocol specified sites of disease is warranted. In randomized comparative trials in particular, the scheduled assessments should be performed as identified on a calendar schedule (for example: every 6–8 weeks on treatment or every 3–4 months after treatment) and should not be affected by delays in therapy, drug holidays or any

other events that might lead to imbalance in a treatment arm in the timing of disease assessment.

2.6 CONFIRMATORY MEASUREMENT/DURATION OF RESPONSE

2.6.1 Confirmation

In non-randomized trials where response is the primary endpoint, confirmation of PR and CR is required to ensure responses identified are not the result of measurement error. This will also permit appropriate interpretation of results in the context of historical data where response has traditionally required confirmation in such trials [2]. However, in all other circumstances, i.e. in randomized trials (phase II or III) or studies where stable disease or progression are the primary endpoints, confirmation of response is not required since it will not add value to the interpretation of trial results. However, elimination of the requirement for response confirmation may increase the importance of central review to protect against bias, in particular in studies which are not blinded.

In the case of SD, measurements must have met the SD criteria at least once after study entry at a minimum interval (in general not less than 6–8 weeks) that is defined in the study protocol.

2.6.2 Duration of overall response

The duration of overall response is measured from the time measurement criteria are first met for CR/PR (whichever is first recorded) until the first date that recurrent or progressive disease is objectively documented (taking as reference for progressive disease the smallest measurements recorded on study).

The duration of overall complete response is measured from the time measurement criteria are first met for CR until the first date that recurrent disease is objectively documented.

2.6.3 Duration of stable disease

Stable disease is measured from the start of the treatment (in randomized trials, from date of randomization) until the criteria for progression are met, taking as reference the smallest sum on study (if the baseline sum is the smallest, this is the reference for calculation of PD).

Appendix 8 Modified RECIST v1.1 for Immune-Based Therapeutics (iRECIST)

Conventional response criteria may not be adequate to characterize the anti-tumor activity of immunotherapeutic agents, which can produce delayed responses that may be preceded by initial apparent radiographic progression, including the appearance of new lesions. Therefore, immunotherapy-specific response criteria adaptations to Response Evaluation Criteria in Solid Tumors, Version 1.1 (RECIST v1.1; Eisenhauer et al 2009) have been developed to allow for unconventional response and progression patterns. These include modified RECIST v1.1 for immune-based therapeutics (iRECIST; Seymour et al 2017), which was developed by the RECIST working group in an effort to create a common set of criteria that the cancer immunotherapy field could apply to clinical trials.

Response evaluation through use of iRECIST requires collection of tumor assessment data after radiographic progression per RECIST v1.1. Details regarding lesion evaluation are described below. When not otherwise specified, RECIST v1.1 conventions will apply.

Criteria for determining overall response at a single timepoint per iRECIST are also summarized below. Of note, overall response per iRECIST will not be captured in the electronic Case Report Form (eCRF), but will instead be calculated programmatically by the Sponsor on the basis of investigator-assessed individual lesion data recorded in the eCRF.

iRECIST response status is not a specific component of treatment discontinuation criteria, including decisions about whether to continue treatment beyond progression per RECIST v1.1. Investigators should instead take into account radiologic data and clinical status in making such decisions

EVALUATION OF LESIONS TO SUPPORT IRECIST RESPONSE ASSESSMENT AFTER DISEASE PROGRESSION PER RECIST V1.1

iRECIST is an extension of RECIST v1.1 that allows for response assessment following disease progression per RECIST v1.1. RECIST v1.1 rules for categorizing lesions as measurable or non-measurable and measuring lesions (see Appendix 7) also apply to iRECIST. After disease progression per RECIST v1.1, the same target and non-target lesions selected at baseline will continue to be followed, along with any new lesions that develop, to support iRECIST response evaluations, as described below and summarized in Table 1. Once a lesion has been categorized as a target, non-target, or new lesion, it will remain classified as such.

TARGET LESIONS

The target lesions selected at baseline should continue to be measured at all tumor assessment timepoints after disease progression per RECIST v1.1, according to RECIST v1.1 conventions.

NON-TARGET LESIONS

Non-target lesions selected at baseline should continue to be followed at all tumor assessment timepoints after disease progression per RECIST v1.1. At each timepoint, non-target lesions should continue to be categorized as "absent" (complete response [CR]), "unequivocal progression" relative to baseline (progressive disease [PD]), or "present without unequivocal progression" (non-CR/non-PD), as defined by RECIST v1.1. In addition, any non-target lesions that were categorized as PD at the previous timepoint should be evaluated to determine whether there has been any further increase in size.

NEW LESIONS

New lesions identified after baseline will be evaluated for measurability with use of the same criteria applied to prospective target lesions at baseline per RECIST v1.1 (e.g., non–lymph node lesions must be \geq 10 mm on the longest diameter; new lymph nodes must be \geq 15 mm on the short axis [see note below]). All new lesions (measurable or non-measurable) must be assessed and recorded at the time of identification and at all subsequent tumor assessment timepoints.

Up to a maximum of five measurable new lesions total (with a maximum of two lesions per organ) should be selected and measured at each timepoint. New lesions that are not measurable at first appearance but meet measurability criteria at a subsequent timepoint should be measured from that point on, if the maximum number of measurable new lesions has not been reached. However, for calculation of the sum of diameters for new lesions, iRECIST excludes measurements from new lesions that were not measurable at first appearance.

All non-measurable new lesions (including those that subsequently become measurable) and additional measurable new lesions (in excess of five total or two per organ) should be assessed to determine whether there is any increase in size relative to the previous assessment timepoint.

Note regarding new lymph node lesions: If at first appearance the short axis of a lymph node lesion is ≥ 15 mm, it will be considered a measurable new lesion. If at first appearance the short axis of a lymph node lesion is ≥ 10 mm and < 15 mm, the lymph node will not be considered measurable but will still be considered a new lesion and should be identified as a non-measurable new lesion. If at first appearance the short

axis of a lymph node is < 10 mm, the lymph node should not be considered pathological and should not be considered a new lesion. A lymph node can subsequently become measurable, when the short axis is \geq 15 mm. Measurable new lymph node lesions should continue to be measured at all subsequent timepoints, even if the short axis decreases to < 15 mm (or even < 10 mm).

Table 1 Guidelines for Evaluation of Lesions to Support iRECIST Response Assessment after Disease Progression per RECIST v1.1

Lesion Type	Evaluation of Lesions to Support iRECIST Response Assessment after Disease Progression per RECIST v1.1		
Target lesions	Measurements should be continued according to RECIST v1.1 conventions.		
Non-target lesions	Non-target lesions should continue to be categorized as absent (CR), unequivocal progression (PD), or present without unequivocal progression (non-CR/non-PD), as defined by RECIST v1.1. In addition, any non-target lesions that were categorized as PD at the previous timepoint should be evaluated to determine whether there has been any further increase in size.		
New lesions	New lesions should be evaluated for measurability per RECIST v1.1.		
	 All new lesions (measurable or non-measurable) must be assessed and recorded at the time of identification and at all subsequent tumor assessment timepoints. 		
	Up to a maximum of five measurable new lesions total (with a maximum of two lesions per organ) should be selected and measured at each timepoint.		
	All non-measurable new lesions (including those that subsequently become measurable) and additional measurable new lesions (in excess of five total or two per organ) should be assessed to determine whether there is any increase in size relative to the previous assessment timepoint.		

CR=complete response; PD=progressive disease; RECIST v1.1=Response Evaluation Criteria in Solid Tumors, Version 1.

SUMMARY OF CRITERIA FOR OVERALL RESPONSE AT A SINGLE TIMEPOINT

Appendix 9 Correction Formulas for QTc Intervals

Fridericia's correction for QTc Measurement - QTcF

QT (ms)
$$\frac{\text{QT (ms)}}{\sqrt[3]{RR(ms)/1000}}$$

QTcF of a subject with a QT of 386 ms and a RR of 848 ms Example:

QT (ms) = 386

RR (ms) = 848

QT (ms) = 408 ms
$$\sqrt[3]{RR(ms)/1000}$$

Bazett's correction for QTc Measurement - QTcB

QT (ms)
$$\frac{\text{QT (ms)}}{\sqrt{RR(ms)/1000}}$$

Example: QTcB of a subject with a QT of 386 ms and a RR of 848 ms

QT (ms) = 386

RR (ms) = 848

$$\frac{\text{QT (ms)}}{\sqrt{\text{RR(ms)}/1000}} = 419 \text{ ms}$$

Appendix 10 Modified Continuous Reassessment Method with Escalation with Overdose Control Design

This appendix provides details of the design that will guide the monotherapy doseescalation stage of this study and examines its operating characteristics through simulations. All analyses were performed using the R statistical software R version 3.4.2.

RATIONALE FOR MODEL BASED DESIGN

The modified Continuous Reassessment Method (mCRM) design uses a statistical model that actively seeks a dose level close to the maximum tolerated dose (MTD) by using toxicity data from all enrolled evaluable patients to compute a precise dose-toxicity curve. It locates the MTD efficiently and minimizes the number of patients treated at possibly pharmacological inactive dose levels. Such model-based designs have been successfully applied in many Phase I dose escalation studies (Schöffski et al 2004; Le Tourneau et al 2009; Neuenschwander et al 2008). The simulations in this appendix investigate the operating characteristics of the design as implemented for this study. In this design the MTD is defined as the dose maximizing the posterior probability that the DLT rate, $\pi(MTD) \in [0.2, 0.35]$ while keeping the probability of overdose $P\{p(MTD) > 0.35\} < 0.25$

STATISTICAL MODEL

A two-parameter logistic model will be used to fit the dose-toxicity relationship.

The probability of DLT at dose d_i , $p(d_i)$ is defined as (1)

$$p(d_j) = \frac{exp(\alpha + \beta x_j)}{1 + exp(\alpha + \beta x_j)}$$
 (1)

where

$$x_j = ln\left(\frac{d_j}{d^*}\right)$$

and d^* is the reference dose (in this case $d^*=70$ mg).

The model (1) thus can be rewritten as (2):

$$ln\left(\frac{p(d_j)}{1 - p(d_j)}\right) = \alpha + \beta x_j \tag{2}$$

where α and β are the parameters to be estimated and assumed to follow a bivariate normal distribution.

Model Prior

A minimally informative bivariate normal prior for the parameters of the DLT-dose response curve (α, β) is constructed in order to have a weak impact to the final MTD determination (Neuenschwander et al. 2008).

The parameters of the minimal informative prior are listed below (3):

$$\mu = (\alpha, \beta) = (-1.736, 0.326)$$

$$\Sigma = \begin{pmatrix} \sigma_{\alpha}^{2} & \sigma_{\alpha\beta} \\ \sigma_{\alpha\beta} & \sigma_{\beta}^{2} \end{pmatrix} = \begin{pmatrix} 0.8948 & 0.1859 \\ 0.1859 & 0.0747 \end{pmatrix}$$
(3)

where μ and Σ are the parameters of the bivariate normal distribution.

The prior distribution used to determine the dose-escalation decision for this study is shown in Figure 1.

[figure not shown]

Figure 1. Minimally informative prior

Maximum Dose-Increments

The following rules for selecting the maximum allowed dose increment will be applied.

Maximum Dose-Increments Relative to Dose Levels

In absence of DLT, the maximum allowable dose-increment will be 200% (i.e. next dose could be as high as 3 fold as previous one) for dose-levels < 700 mg and 100% (i.e. 2 fold) for dose-levels \ge 700 mg

Maximum Dose-Increments Relative to DLT

In case of one event of DLT in a dose-level, the maximum allowable dose increment becomes 100% (i.e. 2 fold), while in presence of 2 DLTs an increment of 50% is allowed (i.e. 1.5 fold).

After the two rules have been applied the maximum allowed dose increment will be defined as the lower increment of the two resulting increments.

Stopping Rules

The algorithm will recommend stopping the trail if any of the following applies:

- Maximum number of patients: stop if the maximum sample size of 60 pts have been reached OR
- Enough information on MTD: at least a minimum of 12 pts enrolled and at least 6
 patients have been accrued near the MTD dose (where near means differing from
 the MTD by at most 15%) and the probability that the MTD dose lies within the
 target toxicity interval is above 50% OR
- Maximum dose is safe: at least a minimum of 6 pts have been accrued at the
 maximum dose or near (differing from the maximum dose by at most 5%) and it is
 at least 50% likely that the probability of a DLT for that maximum dose is below
 20%.

Dose Grid

The following dose grid has been used for the simulations:

- from 30 mg to 100 mg by 2.5
- from 105 mg to 1000 mg by 5
- from 1010 mg to 2100 mg by 10.

MODEL PERFORMANCE EVALUATION

To illustrate how the design will perform, different escalation scenarios are explored and results are tabulated in Table 1. Each row represents different situations: which dose would the model recommend, after seeing no DLTs in previous cohorts and when 0, 1, 2, or 3 DLTs are observed in the current cohort. The evaluation is based on cohort size=3, STOP indicates that the model would stop escalating and the trial would be halted.

Table 1. Dose Escalation Mock Runs

		Model recommendation (and % increment) in case of				
Cohort number	Dose (mg)	0 DLT	1 DLT	2 DLTs	3 DLTs	
1	70	210 (+200%)	80 (+14%)	35 (-50%)	STOP	
2	210	615 (+193%)	220 (+5%)	82.5 (-61%)	45 (-79%)	
3	615	1840 (+199%)	615 (+2%)	225 (-63%)	115 (-81%)	
4	1840	2100 (+14%)	2050 (+11%)	550 (-70%)	255 (-86%)	

As can be seen from the Table above, in general in presence of no DLTs the model will suggest to escalate as the max increments indicate, while in presence of one DLT the increments are really limited. Then, with 2 or 3 DLTs the model always recommends to de-escalate or STOP. Therefore, the results show that the design will adequately adapt the dose in the presence of observed DLTs.

SIMULATION STUDY

A simulation study is conducted to evaluate the operating characteristics for the chosen design parameters (priors, reference dose, stopping rules) under various dose-toxicity scenarios.

[figure not shown]
Dose-Toxicity Scenarios

The different scenarios have been selected in order to cover a wide range of dosetoxicity possibilities and to be able to quantify the risk and benefit, should these scenarios actually occur.

As shown in Figure 2, we explore 8 scenarios. The first 7 represent decreasing levels of toxicity, while the last one considers the toxicity depicted in the prior as true toxicity.

Some scenarios are really extreme, but still they will be informative on how the model would eventually perform, despite the likelihood of the scenario remains extremely low.

Figure 2. True Dose-Toxicity Scenarios: [Scenario number]: dose range corresponding to target toxicity.

Simulation Results

For each of the scenarios, 1000 trials were simulated and in all cases the starting dose of 70 mg was assumed.

The design is evaluated using the following criteria: the MTD chosen, the number of subjects treated at doses higher than the MTD and the total number of subjects treated. For each criterion, we report in Table 2 the median (and 10th 90th percentiles) from the 1000 simulations.

Table 2. Median (and 10th 90th percentiles) from the 1000 simulations

Scenario	Target Dose Interval in True Scenario	Overall N of Patients	N Patients Treated above Target Toxicity Interval	Proportions of DLTs in the trials	Doses selected as MTD
1	10-30	6 (3,15)	6 (3,15)	66.7% (41.7%, 100%)	0 (0,0)
2	300-350	21 (15,27)	6 (3,9)	23.8% (19%, 27.8%)	280 (220,360)
3	500-750	24 (18,33)	3 (0,12)	20.8% (18.5%, 25%)	512.5 (365,765)
4	500-1500	27 (24,36)	6 (3,9)	19% (12.3%, 25%)	572.5 (230,1310)
5	1000-1200	27 (24,36)	6 (3,9)	18.5% (16.7%, 22.2%)	935 (735,1170)
6	1800-2000	36 (27,42)	6 (6,12)	12.1% (5.1%, 18.5%)	2000 (1350,2100)
7	3500-7000	39 (30,51)	0 (0,0)	4.2% (0%, 11.1%)	2100 (2100,2100)
8	204-2142	21 (6,39)	0 (0,0)	23.8% (16.7%, 50%)	215 (0,711)

From these simulations, we see that the design is able to provide a reliable estimate of the MTD: usually, the median of the doses selected as MTD is within the target toxicity dose range. Only in case the toxicity curve is very steep (e.g. Scenario 5) the median might lie just below the target toxicity, which means that we are conservative.

At last, in case of very low toxicity (dose range of target toxicity between 3500 and 7000 mg), the maximum dose is selected as MTD.

In addition, we see that we the number of patients treated over the dose toxicity interval is quite limited, with the exception of the first scenario where —by definition since all doses were too toxic- all pts were treated above the target toxicity.

The good performances of the algorithm are also confirmed by the median number of DLTs observed in the simulations, which is always <25% (again, Scenario 1 is an exception).

Finally, also the sample size required seems to be reasonable: the median number of patients required to give an MTD recommendation is maximum 39 patients across all scenarios. In case of too high toxicity, the required number of treated patients is even lower.

REFERENCES

Schöffski P et al. Phase I trial of intravenous aviscumine (rViscumin) in patients with solid tumors: a study of the European Organization for Research and Treatment of Cancer New Drug Development Group. Annals of Oncology 2004;15: 1816–1824.

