4.3 SCIENTIFIC RATIONALE FOR STUDY DESIGN

The study rationale is provided in Section 2.1.

For Part A, RO7121661 dose escalation will be carried out according to a mCRM with EWOC design and will be based on the occurrence of DLTs.

The mCRM EWOC design has many favorable characteristics:

- It adaptively fits a dose DLT response curve by incorporating toxicity data from eligible participants among different cohorts, and preclinical or clinical information from compounds with similar modes of action via the prior.
- The design also locates the MTD efficiently without pre-specifying exact dose levels for each cohort. Dose selections are made based on the DLT dose response curve measured by a 2 parameter logistic model over the dose range, subject to clinical judgment and mandated safety constraints that limit the size of dose increments. Moreover, the EWOC algorithm highly reduces risks of exposing

participants to overly toxic doses. Of note, the model provides only the upper limit for recommended dose. A dose less than the model recommended dose may be selected based on clinical judgment.

Such model based designs have been successfully applied in many Phase I dose escalation studies (Schöffski et al 2004; Le Tourneau et al 2009; Neuenschwander et al 2008).

In addition, hypothetical dose escalation runs using the design and simulations demonstrate the validity of the parameters of the design as implemented for this study (Appendix 10).

For Part B, RO7121661 will be administered at the determined MTD/RDE to specific participant populations in expansion cohorts. From the data available from Part A, a dosing regimen of 2.1 g Q2W was selected as the dose for Part B expansion cohorts. Please refer to Section 4.4 for further rationale.

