PFS will be defined as the time from study treatment initiation (Cycle 1 Day 1) to the first occurrence of documented disease progression (based on RECIST Version 1.1 Investigator's assessment) or death from any cause, whichever occurs first. For

participants who do not have documented progressive disease or death during the study, PFS will be censored at the day of the last tumor assessment.

Sensitivity analyses of response endpoints (ORR, DRC, DoR, and PFS) may include the evaluation of response according to iRECIST.

OS is defined as the time from the first dose of study treatment to the time of death from any cause. Participants who are still alive at the time of analysis will be censored at the time of their last study assessment (for active participants) or at the last date known alive (for participants in follow-up).

9.4.3 Safety Analyses

Unless otherwise specified all safety analyses listed in Table 9 will be based on the safety population. All safety parameters will be analyzed using descriptive statistics, summarized and presented in tables. Data will be summarized by dose and regimen (if applicable) within each part.

Safety will be assessed through summaries of DLTs (for Part A), adverse events, changes in laboratory test results, changes in vital signs and ECGs, and exposure to study treatment.

Table 9 Safety Statistical Analysis Methods

Endpoint	Statistical Analysis Methods
AEs	The original terms recorded on the eCRF by the Investigator for AEs will be coded by the Sponsor.
	For classification purposes, preferred terms will be assigned by the Sponsor to the original terms entered on the eCRF, using the most up-to-date version of the MedDRA terminology for AEs and diseases. AEs will be graded according to NCI CTCAE grades v5.0.
	Adverse events will be summarized by mapped term and appropriate thesaurus level. Toxicity grade, seriousness, and relationship to study treatment will be presented, as well as summaries of deaths, AEs leading to death and premature withdrawal from study treatment. Glossary of AEs, medication, and procedures will be provided.
Nature and frequency of DLTs	DLT events will be presented by individual listings. The MTD will be estimated with a mCRM–EWOC using DLT-evaluable participants. The MTD estimate will be presented along with 90% Credible Intervals.

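### Appendix 10, Table 2: under the printed rules, scenario 7's sample sizes contradict the DLT shares in the same row, and scenario 8's lower tail for N is not reached

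*Combined protocol and SAP*

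**What the plan says.** Section 4.3 (Scientific Rationale for Study Design) relies on Appendix 10: "hypothetical dose escalation runs using the design and simulations demonstrate the validity of the parameters of the design as implemented for this study". Appendix 10 prints the prior, the dose grid, the limits on dose increments and three stopping rules. The third rule opens "Maximum dose is safe: at least a minimum of 6 pts have been accrued at the" and goes on to require that these patients be at, or within 5% of, the maximum dose. It also asks for at least a 50% posterior probability that the DLT rate there is below 20%. For the mock runs in Table 1, "The evaluation is based on cohort size=3".

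Table 2 gives medians with 10th and 90th percentiles over 1000 simulated trials for each of eight scenarios:

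| Scenario | N | DLT share |
|---|---|---|
| 6 | 36 (27, 42) | 12.1% (5.1%, 18.5%) |
| 7 | 39 (30, 51) | 4.2% (0%, 11.1%) |
| 8 | 21 (6, 39) | 23.8% (16.7%, 50%) |

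On the scenario 8 curve the text says "the last one considers the toxicity depicted in the prior as true toxicity". It sums up sample size as "the median number of patients required to give an MTD recommendation is maximum 39 patients across all scenarios".

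**The concern.** In a trial with few DLTs, the third stopping rule should end escalation soon after the second cohort at 2100 mg. Scenario 7 reports DLT shares so low that many of its trials can have had no DLT, yet its sample sizes are about twice what such a trial should need.

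At stake is the evidence offered for the design. If Table 2 cannot be obtained from the rules printed beside it, a reader cannot tell which design the simulations describe. The sentence on the largest median sample size rests on scenario 7, and low toxicity is the setting closest to what Part A observed: one DLT and no MTD (Sections 2.3 and 4.4).

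**Working it through.** **Inputs (Appendix 10).** Two-parameter logistic model in ln(dose/70); bivariate normal prior with mean (-1.736, 0.326), variances 0.8948 and 0.0747, covariance 0.1859. The dose chosen maximises P(DLT rate in 0.20-0.35) subject to P(rate > 0.35) < 0.25. Increments are at most 3-fold below 700 mg and 2-fold from 700 mg, falling to 2-fold after one DLT and 1.5-fold after two. Start at 70 mg; maximum N 60.

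**Cohort size.** Three is stated for Table 1 only. Table 2 is consistent with it: all 24 N values are multiples of 3, 13 of them are odd (which excludes cohorts of 6 throughout), and scenario 1 has a 10th percentile of 3.

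**Check of the recoded design.** All 16 cells of Table 1 are reproduced within 15%. The prior-mean curve reaches a 20% DLT rate at 70 × exp[(-1.386 + 1.736)/0.326] = 205 mg and 35% at 70 × exp[(-0.619 + 1.736)/0.326] = about 2153 mg, against 204-2142 mg in Table 2.

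**Stopping sizes by number of DLTs, all paths enumerated, cohorts of 3.** The text ties the one-DLT limit to a dose level but does not say this for the two-DLT limit, so both ways of counting are shown.

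| DLTs in trial | Counted per dose level | Counted across the trial |
|---|---|---|
| 0 | 18 | 18 |
| 1 | 18 or 21 | 18, 21 or 24 |
| 2 | 18 to 30 | 18 to 42 |

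If only the two-DLT limit is counted across the trial, one-DLT trials still stop at 18 or 21, and two-DLT trials run up to 42.

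Using Table 1's doses, the zero-DLT path is 70, 210, 615, 1840, 2100, 2100 mg. At N = 18 there are 6 patients at 2100 mg and P(DLT rate < 20%) = 0.97, where 0.50 is required.

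**Scenario 7, 10th percentile.** With N at most 60, the smallest non-zero share is 1/60 = 1.7%, so a printed 0% means no DLT. At least about 10% of trials then had none and stopped at 18. The 10th percentile of N is at most 18; Table 2 gives 30.

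**Scenario 7, median.** At least half the trials have a share of 4.2% or less. The candidates are:
- 0 DLTs: N = 18.
- 1 DLT: needs N of at least 24 (1/24 = 4.17%), which occurs only if both limits are counted across the trial.
- 2 DLTs: needs N of at least 48 (2/48 = 4.17%), above the maximum of 42.
- 3 DLTs: needs N of at least 72, above the limit of 60; more DLTs need still more.

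Median N is therefore at most 18, or 24 under the most generous counting. Table 2 gives 39. Neither step uses a true curve.

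**Scenario 8.** A trial stops by N = 6 only after 3/3 DLTs at 70 mg; 2/3 and then at least 2/3 at about 35 mg; or 1/3 and then 3/3 at about 80-85 mg. All these doses lie below 204 mg, so on an increasing curve each DLT rate is at most 20%:

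P(N ≤ 6) ≤ 0.008 + 0.096 × 0.104 + 0.384 × 0.008 = 0.021.

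The prior-mean curve itself gives 0.7%. A 10th percentile of 6 needs at least 10%. Simulated N is 24-27 with a 10th percentile of 15.

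**Scenario 6.** Counted per dose level, only 0/18 and 1/21 have a share of 5.1% or less, so the 10th percentile of N could not exceed 21 (27 stated). If the two-DLT limit is counted across the trial, 2/39 = 5.1% occurs and the bound is lost. The simulated median is 24-30 against 36, but on an assumed curve.

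**The case against.** The strongest reply is that Table 2 may have been run with settings the appendix does not print. The cohort size in the main text is blanked in the public version, which is not a fault of the plan, and the appendix states 3 only for Table 1. A stop when no dose is admissible is used in Table 1 (3/3 at 70 mg) but not listed. Other unprinted rules are conceivable. Holding each level until 6 patients are treated would move the zero-DLT stop to 30 and bring scenario 7 closer, although it still misses 39 and fits scenarios 3-5 worse. This stands as an explanation, but it does not reconcile the printed rules with the printed table.

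The ambiguity in the DLT limits also stands. A reader might infer that the exact figure of 18 is forced, that shares of 4.2% and 5.1% can never arise, or that scenario 6 is disproved in the same way as scenario 7. The documents do not support any of these: 1/24 and 2/39 occur under one reading of the limits, and the scenario curves are in a figure that is not shown.

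For scenario 8, the ceiling assumes one fixed curve and a toxicity stop inferred from Table 1. If curves were drawn from the prior instead, P(N ≤ 6) would be 4.5%, still short of 10%. Its median DLT share agrees with Table 2, and its median N is only moderately off (21 against 24-27).

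Finally, the 2.1 g dose rests on Part A tolerability and PK (Section 4.4), not on Table 2.

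**Conclusion.** Scenario 7 is wrong as written, given cohorts of 3 and the printed rules. Its 10th-percentile N is at most 18 (30 stated) and its median at most 18 to 24 (39 stated), under every reading of the DLT limits and for any true curve. Scenario 8's 10th-percentile N of 6 is also not reached for the fixed prior-mean curve that gives the stated target interval: about 2% of trials at most, where 10% are needed. Scenario 6 is a query.

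A reader might go further and infer a coding error, an unsafe escalation or a doubtful expansion dose. The documents do not support that. The cause is unknown, scenario 7 overstates rather than understates sample size, scenarios 2-5 come within two cohorts on median N (with assumed curves), and escalation is complete. What fails is the claim that these operating characteristics belong to the printed design.

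**What to change.** Reconcile Table 2 with the printed rules in one of two ways:
- rerun it under those rules; or
- state in Appendix 10 the cohort size and every rule actually simulated, including the stop when no dose is admissible and whether DLTs are counted per dose level or across the trial for the increment limits.

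Then restate scenarios 7 and 8 (and 6 if it changes), the sentence giving 39 as the largest median, and the reliance on the simulations in Section 4.3. A corrected table or a note in the study report would do.

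The cost is statistician time for one simulation run. It needs no patients, no new data and no change to the pre-specified model, but the restated operating characteristics may differ from those now in the protocol.
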